## Study Design Summary

Study Type:	Experimental
Estimated Enrollment:	3060 participants
Observational Model:	Cohort
Time Perspective:	Prospective
Official Title:	
Estimated Study Start Date:	September 2020
Estimated Primary Completion Date:	December 2021
Estimated Study Completion Date:	January 2022

## Study Population:

The study population consists of a diverse group of Stanford faculty, staff, and students, and the local Santa Clara County community and specific external sources with known positive saliva samples and DUA/MTA in place. More specifically, there are three sub-populations to address our aims:

- 1) (Positive population) Hospitalized patients (N=15)
- 2) (High risk and positive population) People from Bay area community and external sites with known positive saliva samples and DUA/MTA in place; Those with a suspected COVID infection seeking testing within the Stanford Health Care system (N=1500)
- 3) (Low risk population) People from Bay area community; Students on the Stanford campus and employees at Stanford Health Care (N=1500)

## Criteria for Hospitalized Patients

### Inclusion Criteria

- $\geq 18$  years
- Hospitalized at Stanford Health Care for COVID-related complications and tested positive for SARS-CoV-2 with a PCR-based test
- Able to understand and consent to study and with a clinical trajectory likely to be consistent with multi-day participation

### Exclusion Criteria:

- Participants with salivary gland dysfunction (including patients with Sjogren's disease or those with xerostomia associated with lupus or rheumatoid arthritis)
- Participants will not be eligible if they identify any reason they are unable to participate in the study

## Criteria for High Risk and Positive Population

### Inclusion Criteria:

- $\geq 18$  years
- Seeking testing for suspected COVID or a participant in a study of COVID-positive outpatients or from external sites with known positive saliva samples and DUA/MTA in place
- Own an internet-enabled phone or device capable of loading web pages, receiving text messages, and taking/uploading photos.
- Willing to participate in the study for one month

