**Exclusion Criteria:**

- Participants with prior confirmed SARS-CoV-2 infection
- Participants who have color blindness
- Participants unable to operate the SnapDx device
- Participants with salivary gland dysfunction (including patients with Sjogren's disease or those with xerostomia associated with lupus or rheumatoid arthritis)
- Participants will not be eligible if they identify any reason they are unable to participate in the study

**Study Location:** Stanford University Campus, Stanford Health Care, Stanford affiliated COVID-19 testing sites (including drive through testing sites). We will accept deidentified and inactivated saliva samples from external sources with DUA/ MTA in place and IRB approval.

**Funding:** Stanford Medicine Catalyst

**DUA , MTA OTL:** We have DUA in place with a site in Guatemala and will have DUA/ MTA in place for the sharing of saliva samples from any/all sources as they become available.

**Mobile Medical Website/App:** REDCap  
**DRA:** N/A or previously approved for Pattern Health

**IND Exempt:** Yes, observational diagnostic tool

**Manufacturer:** N/A

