**Analysis Sets:**

There are two key analysis sets that are subsets of the study population. The first subset consists of outpatients. The second subset consists of the patients hospitalized for COVID-related complications who will be tested daily for 5 days.

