### **Analysis of the Validity Outcomes**

The sensitivity, specificity, positive predictive value (PPV), and negative predictive value (NPV) of the test will be estimated using the results collected in outpatients. The results of the PCR-based test will be the gold standard used to estimate the test's diagnostic accuracy. Home test results will only be included in this analysis if the test is performed within 24 hours of the time the swab used in the PCR tests was collected.

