### **Recruitment:**

The study will recruit up to 3060 participants including 60 hospitalized patients from multiple locations. These will include SHC COVID testing sites, Stanford Health Care

300 and 500P locations (the Emergency Department and other in-patient wards particularly M7, the COVID ward), as well as the front entrance of Stanford hospital and several locations on Campus. We will also be recruiting folks from the bay area community for our study. Participants will fall into two categories: i) those receiving a CLIA certified nasal swab COVID-19 test at SHC at the moment of recruitment, and ii) those not.

We will be recruiting a high-risk population because we will be recruiting from a pool that includes people who are seeking medical attention and/or participating in COVID-related research studies. Feasibility and validity of the tests will be evaluated in the high-risk population. We will be additionally recruiting a low-risk population to assess feasibility in the general population. Hospitalized patients will provide information on concordance between the CLIA COVID test and the home saliva test in patients over a five day period when we expect to see a mix of positive and negative tests.

To increase the number of SARS-CoV-2 positive saliva samples, we will accept deidentified and deactivated saliva samples from external sources, including Guatemala. All of these external sources will have DUA/MTA in place and will have institutional approval and have received written informed consent from all participants for the local trials, including the sharing of these samples with Stanford University for the current trial.

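### The plan does not say whether external known-positive saliva samples count towards outpatient accuracy and the 85% threshold, and it takes PPV and NPV from a set enriched by design

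*Combined protocol and SAP*

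**What the plan says.** **Who is in the group.** Under Study Population, the second sub-population (N=1500) includes "People from Bay area community and external sites with known positive saliva samples and DUA/MTA in place". The inclusion criteria for that group list three alternative routes: seeking testing for suspected COVID, taking part in a study of COVID-positive outpatients, or coming "from external sites with known positive saliva samples and DUA/MTA in place". Recruitment gives the purpose: "To increase the number of SARS-CoV-2 positive saliva samples, we will accept deidentified and deactivated saliva samples from external sources, including Guatemala". The Study Location paragraph describes the material: "We will accept deidentified and inactivated saliva samples from external sources with DUA/ MTA in place and IRB approval". No number of external samples is given.

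**Where they would be analysed.** Recruitment says validity is assessed in the high-risk population. Analysis Sets names two sets: "The first subset consists of outpatients", and the other is the hospitalized patients tested daily for five days. Analysis of the Validity Outcomes says that sensitivity, specificity, PPV and NPV "will be estimated using the results collected in outpatients". PCR is the reference, and only home tests done within 24 hours of the swab are admitted.

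**Two other comparisons with PCR.** Analysis of the Feasibility Outcomes, also in outpatients, compares SnapDx with PCR and sets success at 80% overall agreement and 85% agreement in positives. It has no 24-hour rule and does not say whether the PCR is on swab or saliva. The Validity part of Study Design compares SnapDx with saliva direct PCR to give PPA and NPA, but that comparison does not reappear under Statistical Considerations.

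**The concern.** A saliva test can miss a swab-positive infection because the virus is not detectable in that person's saliva. Samples chosen because the saliva is positive contain no such cases. Counted against a swab reference, they raise positive agreement without any change in the test, and the rise grows with their share of the positives. The plan sets no limit on that share, and one success threshold (85% in positives) is a statement about positives.

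PPV and NPV have a second, simpler problem. Both depend on prevalence, and the outpatient set is deliberately loaded with positives. Figures from it do not describe the home surveillance use that the Rationale has in mind.

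**Working it through.** The documents state no expected sensitivity, specificity, prevalence or external share, so there is no figure of the plan's to reproduce. All inputs below are assumptions except the 85% threshold and the outpatient total of 1500 + 1500 = 3000.

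**1. Can external samples reach each analysis?**
- *Validity analysis (swab reference).* The 24-hour rule, read literally, would drop most of them. They are inactivated samples from elsewhere, and under the Validity part of Study Design collected saliva is run by five trained users. The external share is then near zero.
- *Feasibility thresholds.* Nothing in the text keeps them out.
- *Missing data.* Outpatient data are multiply imputed, and PCR results that cannot be linked are given as an example of missing data. Whether an external sample without a swab is excluded or imputed is not stated.

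**2. Effect on positive agreement against a swab.** Let s = P(saliva positive | swab positive), a = P(SnapDx positive | saliva positive), b = P(SnapDx positive | swab positive, saliva negative), and w = external share of the positives. I read positive agreement as SnapDx positives among the PCR positives.

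- Local: L = s·a + (1 − s)·b
- Pooled: (1 − w)·L + w·a
- Bias: w·(a − L)

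With a = 0.90 and b = 0.02:

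| s | L (w = 0) | pooled, w = 0.50 | bias at w = 0.50 |
|---|---|---|---|
| 0.80 | 0.724 | 0.812 | 0.088 |
| 0.85 | 0.768 | 0.834 | 0.066 |
| 0.90 | 0.812 | 0.856 | 0.044 |
| 0.95 | 0.856 | 0.878 | 0.022 |

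Setting b = 0 changes little: at s = 0.80 the bias is 0.5 × (0.90 − 0.72) = 0.090.

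**3. Can this decide the 85% threshold?** At s = 0.85 the threshold is reached when w = (0.85 − 0.768)/(0.90 − 0.768) = 0.082/0.132 = 0.62. At s = 0.80 it takes w = 0.126/0.176 = 0.72, and at s = 0.90 it takes w = 0.038/0.088 = 0.43. At s = 0.95 the local value already passes. So in part of the assumed range the external share alone decides the result. The 80% overall threshold need not move the same way: external positives pull overall agreement towards a, which can lower it when most records are negatives read correctly.

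**4. PPV and NPV.** Assume sensitivity 0.85, specificity 0.98 and 3000 records, of which K are added known positives from any source. Positives = p(3000 − K) + K, where p is the underlying prevalence.

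| p | K | PPV | NPV |
|---|---|---|---|
| 2% | 0 | 0.464 | 0.997 |
| 2% | 100 | 0.703 | 0.992 |
| 2% | 300 | 0.850 | 0.980 |
| 5% | 0 | 0.691 | 0.992 |
| 5% | 100 | 0.791 | 0.987 |
| 5% | 300 | 0.878 | 0.975 |

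For p = 2% and K = 100: positives = 0.02 × 2900 + 100 = 158, negatives = 2842, and PPV = 134.3/(134.3 + 56.84) = 0.703. The test is the same in every row.

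**The case against.** A reader might infer that the plan pools external samples and that its reported sensitivity will therefore be inflated. The documents do not support that, for four reasons.

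1. No section says the samples belong to the outpatient set. The same inclusion criteria require a phone or device and a month of participation, which a deidentified sample cannot provide. Listing under eligibility therefore does not settle analysis-set membership.
2. The 24-hour rule would probably take most of them out of the swab-referenced analysis.
3. The Validity part of Study Design already has a comparison that suits them. Against saliva direct PCR, selection on positive saliva does not by itself inflate PPA. Only a difference in spectrum, such as viral load, would.
4. The plan does not say how external sites established positivity. Elsewhere it speaks of positive saliva samples from people who tested positive by a standard PCR test. If external samples are simply saliva from swab-positive donors, saliva-negative cases are not screened out and the mechanism fails.

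All four points stand, and they make the sensitivity bias conditional. They do not close the gap. The thresholds have no 24-hour rule and name no specimen for the PCR. If the rule does exclude the samples, material collected to add positives has no stated place in the statistical section.

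On PPV and NPV the objection is that external samples are not the main cause. That is correct: participants from a study of COVID-positive outpatients enrich the set with or without them. The 24-hour rule is about timing, so those with a swab inside the window remain.

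**Conclusion.** The concern holds in conditional form. External known-positive samples are assigned to the group in which validity is evaluated, and no rule excludes them from the outpatient set or analyses them separately.

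The upward bias in positive agreement needs two things the documents leave open: that the samples count against a swab reference (in the thresholds or in the validity analysis), and that they were selected on a positive saliva result. Given both, and with s from 0.80 to 0.95 and a = 0.90, the bias is 0 points with no external samples and about 2 to 9 points at a 50% share. These sizes illustrate the mechanism and do not predict this trial's result.

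The PPV and NPV point needs neither condition. Those figures reflect how many known positives were recruited and not the intended-use population. In the illustration at 2% prevalence, 100 added positives raise PPV from 0.464 to 0.703 and lower NPV from 0.997 to 0.992.

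**What to change.** - **Analysis Sets:** define external known-positive samples as a separate stratum outside the outpatient set, and state how each source established positivity (saliva or swab).
- **Analysis of the Validity Outcomes:** exclude that stratum from swab-referenced sensitivity, and report it only as PPA against saliva direct PCR, bringing the comparison from the Validity part of Study Design into the statistical section.
- **Analysis of the Feasibility Outcomes:** exclude the stratum from the 80%/85% thresholds, and name the PCR specimen used there.
- **PPV and NPV:** estimate them only in participants recruited without known infection status, leaving out both external samples and known-positive outpatients. Alternatively, compute them from sensitivity and specificity at stated prevalences, which does not depend on the mix recruited.

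This is a change of wording, with no new data to collect. The cost is precision in the headline sensitivity. As an illustration at s = 0.85 and a = 0.90, 50 local positives give an estimate of 0.768 with a 95% Agresti-Coull interval of 0.633 to 0.865 (width 0.232). Adding 50 external positives gives 0.834 with an interval of 0.748 to 0.895 (width 0.147). The second interval is narrower, but it is centred on a quantity that is not sensitivity against the swab.

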**Exclusion Criteria:**

- Participants who have color blindness
- Participants unable to operate the SnapDx device
- Participants with salivary gland dysfunction (including patients with Sjogren's disease or those with xerostomia associated with lupus or rheumatoid arthritis)
- Participants will not be eligible if they identify any reason they are unable to participate in the study

**Criteria for Low Risk Population****Inclusion Criteria:**

- $\geq 2$  years
- Have access to an internet-enabled phone or device capable of loading web pages, receiving text messages, and taking/uploading photos.
- Willing to participate in the study for one month, or permission and willingness from legal guardian for participants under 18 years old.

**Exclusion Criteria:**

- Participants with prior confirmed SARS-CoV-2 infection
- Participants who have color blindness
- Participants unable to operate the SnapDx device
- Participants with salivary gland dysfunction (including patients with Sjogren's disease or those with xerostomia associated with lupus or rheumatoid arthritis)
- Participants will not be eligible if they identify any reason they are unable to participate in the study

**Study Location:** Stanford University Campus, Stanford Health Care, Stanford affiliated COVID-19 testing sites (including drive through testing sites). We will accept deidentified and inactivated saliva samples from external sources with DUA/ MTA in place and IRB approval.

**Funding:** Stanford Medicine Catalyst

**DUA , MTA OTL:** We have DUA in place with a site in Guatemala and will have DUA/ MTA in place for the sharing of saliva samples from any/all sources as they become available.

**Mobile Medical Website/App:** REDCap  
**DRA:** N/A or previously approved for Pattern Health

**IND Exempt:** Yes, observational diagnostic tool

**Manufacturer:** N/A

## Rationale

Clinical testing for SARS-CoV-2 falls broadly into two categories: molecular testing to detect the genomic sequence of the virus and serology testing for the antibody response of the host. While CLIA based testing in both categories has proved valuable for individual care during the pandemic, the cost (up to \$100 in some cases) and time (a minimum of 12 hours in most cases) required for these approaches mean they have had little public health impact on the pandemic. A home based surveillance test for the presence of SARS-CoV-2 in saliva, that is cheap (a few dollars) and fast (under 40 minutes) would be transformative in the global management of COVID-19. It would allow nothing less than the reopening of schools, businesses, and the safe return of many aspects of society to normal. Individuals could test themselves every morning before heading to work, for example, to demonstrate they were not currently infected. In this protocol, we aim to demonstrate the viability of such an approach in a target population of Stanford employees and students who would test themselves at our research facility and upload the results via a mobile website/app. The protocol includes enrichment for positive samples through a cohort recruited through the Stanford Emergency Department (that would allow calculations of sensitivity required by the US FDA) and CLIA validation of these samples, a collection of known Sars-Cov-2 samples from external sources (including from Guatemala) as well a random selection of negative home tests to allow estimation of specificity. The overall aim is to demonstrate the feasibility, usability, and real-world validity of home surveillance testing at scale to provide the foundation for scaling up to potentially millions of tests around the world.

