## Validity

Saliva samples are to be collected in several patient populations, including from both inpatient and outpatient clinics, and COVID positive or negative patients determined by nasal swab PCR tests from several different locations. We will make a concerted effort to reach out to the Stanford and bay area communities and collect positive saliva samples from those who have tested positive through a standard PCR test. Five intended users will be given basic training to conduct SnapDx tests on these saliva samples as if they were taking the test themselves. A small portion of each saliva sample will also be tested for SARS-CoV-2 using saliva direct PCR in the laboratory. SnapDx test results will be compared against saliva direct PCR results to determine the positive percent agreement (PPA) and negative percent agreement (NPA).

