### *Test description*

[figure not shown]
Test materials: saliva collection tube, small handheld centrifuge, test kit (plasticware) The test kit should be stored in a regular fridge (4C) at the location of the participant - prior to use.

The test materials include a cartridge containing a tube with closed reagents into which the participant will provide the saliva sample. Participants will be asked to provide 1ml of saliva into the collection tube, after which they will close the cap of the cartridge. They will be asked to pour boiling water into a mug and place the tube into the boiling water for 3 minutes. At the end of 3 minutes, they will then place the tube back in the mug of water for 40 minutes. At the end of 40 minutes, they remove the tube and note the color (pink/ orange = negative, yellow = positive). They will take a photograph of the tube against a given white photocard (provided in the kit) and upload it to the website. After filling in the short (<1 minute) symptom questionnaire and the short usability (<20 seconds) questionnaire they will dispose of the tube in the trash.

At that point, **if the test result is negative** (no evidence of infection) then they will be asked to do nothing other than fill in a survey and upload the image of the tube via study app. **If the test result is positive** they will be instructed to behave as if they might be infectious in their home and outside of their home (maximizing the use of masks and distancing) and asked to take a CLIA nasal swab test at their nearest SHC testing site at their earliest opportunity.

Our study provides the option for the participants to take a PCR nasal swab test at Stanford Health Care when their SnapDx tests result or the saliva direct PCR test done by the lab shows a positive SARS-CoV-2 result. Our study will cover the cost of the PCR nasal swab test for the participants.

Figure: Color change in tubes. Yellow color is a positive result

Left sample spiked with random plasmid DNA, right sample spiked with COVID-19 control RNA, at 50 genomes/ $\mu$ L.

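### The sample that the Rationale names for specificity is selected on a negative SnapDx result, and the analysis section neither excludes nor weights it, so specificity can be biased in either direction

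*Combined protocol and SAP*

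**What the plan says.** The Rationale assigns a data source to each accuracy measure. For sensitivity it describes "enrichment for positive samples through a cohort recruited through the Stanford Emergency Department", with CLIA validation, plus known positive samples from external sources. For specificity it names "a random selection of negative home tests to allow estimation of specificity".

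The statistical text is in Analysis of the Validity Outcomes. Sensitivity, specificity and the predictive values "will be estimated using the results collected in outpatients". The reference is PCR: "The results of the PCR-based test will be the gold standard used to estimate the test's diagnostic accuracy". The one inclusion rule concerns timing: "Home test results will only be included in this analysis if the test is performed within 24 hours" of collection of the swab.

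PCR results reach the study by several routes:

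- **At recruitment.** One of the two recruitment categories is "those receiving a CLIA certified nasal swab COVID-19 test at SHC at the moment of recruitment" (Recruitment).
- **After a positive home test.** The participant is "asked to take a CLIA nasal swab test at their nearest SHC testing site at their earliest opportunity" (Test description).
- **On the saliva itself.** "A small portion of each saliva sample will also be tested for SARS-CoV-2 using saliva direct PCR in the laboratory" (Validity). This supports positive and negative percent agreement, in people whose status was set by nasal swab PCR.
- **The random selection of home negatives.** It appears only in the Rationale. Its size, its sampling fraction and the way it joins the other data are not given.

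**The concern.** Specificity is the share of PCR-negative tests that SnapDx also calls negative. It can be learned only from a set in which a PCR-negative test could have read positive. A sample drawn because SnapDx read negative excludes that possibility before PCR is applied. What it does estimate is the share of SnapDx-negatives that are PCR-negative, which is negative predictive value in that group.

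The analysis section does not repair this. A selected home negative with a swab inside the 24-hour window meets its only stated inclusion rule and would enter the specificity denominator. Home positives enter by a different route and at a different rate. The estimate then depends partly on who was swabbed and not only on the assay.

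Specificity is half of the Primary Validity Aim. The Rationale envisages people testing every morning before work, and at that frequency false positives are a main cost of error.

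**Working it through.** **Plan's own figure.** There is none to reproduce: the documents state no target, precision or sample size for specificity.

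**Inputs from the documents.** PCR as reference; outpatients with a swab within 24 hours; 95% Agresti-Coull intervals (General Considerations).

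**Inputs assumed.** True specificity (sp), the fractions verified by PCR, and all counts. They are shown as ranges because the documents give none of them.

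**Step 1: the negative selection alone.** False positives (FP) are 0, so TN/(TN + FP) = TN/TN = 100% for any sp, where TN is true negatives. With an assumed 300 PCR-negative tests, Agresti-Coull gives:

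- adjusted n = 300 + 3.84 = 303.84
- centre = (300 + 1.92)/303.84 = 0.9937
- half-width = 1.96 × √(0.9937 × 0.0063/303.84) = 0.0089
- lower limit = 98.5%

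That limit would be the same for a poor assay and a good one, so it carries no information on specificity.

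**Step 2: negatives and positives verified at different rates.** Among PCR-negative tests, let f be the fraction of home negatives verified and v the fraction of home positives verified. Unweighted pooling estimates

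f × sp / [f × sp + v × (1 − sp)].

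Prevalence does not enter, because everything is conditional on PCR-negative. With sp = 95%:

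| f | v | Calculation | Reported specificity |
|---|---|---|---|
| 0.1 | 1 | 0.095/(0.095 + 0.050) | 65.5% |
| 0.2 | 1 | 0.190/(0.190 + 0.050) | 79.2% |
| 0.5 | 1 | 0.475/(0.475 + 0.050) | 90.5% |
| 0.5 | 0.5 | 0.475/(0.475 + 0.025) | 95.0% |
| 0.5 | 0.1 | 0.475/(0.475 + 0.005) | 99.0% |

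The estimate is too low when f < v, right when f = v and too high when f > v. Either inequality is plausible here. Positives are asked to have a swab while only some negatives are selected, which points to f < v. But the request to positives carries no deadline while the analysis demands 24 hours, which could make the usable v small.

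**Step 3: selected negatives added to an unselected set.** Take m PCR-negative tests verified regardless of the SnapDx result, such as swabs at recruitment, and add k PCR-negative tests from the selection with no matching positives. The pooled estimate is (sp × m + k)/(m + k).

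- sp = 90%, m = 300, k = 300: (270 + 300)/600 = 95.0%
- sp = 90%, m = 300, k = 700: (270 + 700)/1000 = 97.0%
- sp = 95%, m = 500, k = 300: (475 + 300)/800 = 96.9%

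In this arrangement the bias is always upward and grows with k.

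**Step 4: does weighting repair it?** Weight each verified negative by 1/f and each verified positive by 1/v. The estimate becomes (f × TN/f) / (f × TN/f + v × FP/v) = TN/(TN + FP), the true specificity, for any f and v above 0. A negatives-only sample is therefore usable if positives from the same source are also verified and both fractions are known.

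**The case against.** The strongest reply is that the quoted clause is background narrative. The operative analysis is not confined to SnapDx-negative tests, and the selection is not mentioned again. This stands, and it limits the point. A reader might infer from the Rationale that the trial will report 100% specificity by construction. The documents do not support that: swabs at recruitment, swabs after a positive home test and the laboratory saliva PCR each allow a false positive to be seen. The 100% belongs to the selected sample used alone.

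A reader might also infer that pooling must push specificity up. That is not supported either. Inflation needs negatives verified more often than positives, or negatives added to an unselected set. If all positives and only some negatives are swabbed, the estimate falls.

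Two further replies carry less weight:

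- **Multiple imputation.** Handling of Missing Data plans it for outpatients under missing at random, and mentions PCR results that cannot be linked. Imputing PCR from the SnapDx result is a recognised correction for partial verification, but only if unverified tests stay in the data as missing. The 24-hour rule leaves them out, and the two sections are not reconciled.
- **Loose wording.** The clause may have been meant to describe tests from uninfected people. That is possible, but the text says negative home tests, and the home test is the one being evaluated.

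**Conclusion.** The point holds as a mismatch between the Rationale and the analysis section that can bias a primary validity estimate. The only sample named for specificity cannot estimate it alone, and the analysis section has no rule to exclude, separate or weight that sample.

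Neither the size nor the sign of the bias is fixed by the documents. In the scenarios above, a true 95% is reported as anything from 65.5% to 99.0%, and a true 90% as 95% to 97%. These figures illustrate sensitivity to the verification mix; they do not predict the trial's result. They rest on assumed specificities, fractions and counts, on unweighted pooling, on the verified tests being representative within each SnapDx result, and on reading negative home tests literally.

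The negative percent agreement described under Validity is not affected, because people enter that comparison by nasal swab PCR status and not by SnapDx result.

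**What to change.** 1. **Rationale.** Replace the specificity clause with wording such as: a random selection of home tests, chosen without regard to the SnapDx result. State its size or sampling fraction.
2. **Analysis of the Validity Outcomes.** Base primary specificity on tests whose PCR was obtained independently of the SnapDx reading, that is, swabs taken at recruitment. Report the comparison with laboratory saliva PCR separately, since the reference differs.
3. **If a negatives-only sample is kept.** Use it for negative predictive value. Otherwise include it in specificity only together with verified positives from the same source group, each weighted by the inverse of its known sampling fraction. For positives this means recording how many were swabbed within 24 hours, and stating the assumption that they represent the rest.
4. **Handling of Missing Data.** Say whether home tests without a timely swab are excluded or kept with PCR missing and imputed.

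The cost is a few sentences of wording, and no new assay where the planned saliva PCR is used. The downside is fewer eligible pairs and a wider interval for primary specificity. The estimate may move in either direction.
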